The Phase 2 pilot RCT evaluated Listening Visits provided by bachelor's-level NICU nurses as compared with the care currently provided by the NICU social work team. In three specific aims we will assess the relative effectiveness of Listening Visits on depression symptoms, perception of nurse support, and infant's length-of-stay. In March the study was stopped due to the pandemic. The data and safety monitoring committee advised us to complete the analyses of the 45 out of 50 women in the RCT and to modify the RCT to evaluate Listening Visits delivered via telehealth as a feasibility extension. The use of the no cost extension period and funds to evaluate this expanded aim as a modification of the RCT was approved by the study's program officer at the National Institute of Nursing Research. Because recruitment at UIHC is slow, the modification (June 2021) proposed to recruit NICU mothers via the OVIA Health Parenting app.

[name] will review selected audio recordings of the study therapists to determine their fidelity to the treatment model. She is at the Swansea University in Wales and will access a secure university server to listen to these recordings.

Specific Arms:

Specific Aim #1: Compare the effects of LV with usual care (UC) on depressive symptoms as assessed by the Inventory of Depression & Anxiety Symptoms-General Depression Scale (IDAS-GD). Secondarily, the study will compare LV with UC on worry, stress, anxiety, and parent satisfaction with NICU care.

Hypothesis: LV recipients will have significantly lower IDAS-GD total scores than those randomized to UC at 4 & 8 weeks post enrollment.

Specific Aim #2: Compare the effect of LV with UC on perception of nurse support as assessed by the Nurse Parent Support Tool. Secondary analyses will assess relationship of nurse support and depression.

Specific Aim #3 Compare the effect of LV with UC on infant length-of-stay.

Expanded aim: Utilizing the same inclusion/exclusion criteria as the RCT and assessment schedule and instruments, modify the RCT protocol to evaluate the feasibility of delivering Listening Visits virtually, in an open trial design.

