-All LV telehealth participants will be invited to complete 3 study assessments, at enrollment, and 4 and 8 weeks post enrollment. The questionnaires will require approximately between 5-20 minutes to complete. They will be sent via redcap.

-In the event that an infant dies, mothers will not be asked to do further assessments. They may continue with the Listening Visits, up to six sessions, if they wish.

Risks to subjects including

Risk 1. The hospitalization of an infant is a stressful experience and participation in research can be perceived as a burden by some mothers.

Risk 2. Answering questions about mood may be upsetting

Risk 3. Clinical safety screening phase participants. Women who complete the screening phase assessment may score high on the EPDS scale, or have suicidal ideation and they may not be eligible or want to participate in the intervention evaluation phase.

Risk 4. Clinical safety LV telehealth phase open trial. Among study participants, women may experience a clinically significant worsening of mood or symptoms, or suicidal feelings may newly emerge.

Risk 5. Loss of confidentiality of data

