Official Title: Promoting Emotional Well-Being in Distressed NICU (Neonatal Intensive Care Unit) Mothers: A Phase 2 Evaluation of a Nurse-Delivered Approach

NCT Number: NCT03704948

Document Date: 06/22/2021

Promoting Emotional Well-Being in Distressed NICU (Neonatal Intensive Care Unit) Mothers: A Phase 2 Evaluation of a Nurse-Delivered Approach

Statistical Analysis Plan:

RCT: Preliminary Analyses. Chi-square- and t-tests will assess group differences in maternal demographics or infant health status. Missing data (e.g., early dropouts) are accepted by our random regression (mixed model analyses when covariates include variables related to missing data. For the survival analysis, dropouts will be considered as censored. All variables will be assessed for normality and homogeneity of variance (and transformed, as necessary). All randomized participants will be included in the analyses, an "intent-to-treat" approach. Per the Delphi criteria,⁵⁷we will estimate baseline means and measures of variability for all major variables in the study, including confidence intervals, as appropriate.

Specific Aim #1: Compare the effects of Listening Visits with usual care (UC) on depression symptoms as assessed by the Inventory of Depression & Anxiety Symptoms-General Depression Scale (IDAS-GD).

Hypothesis: Listening Visits recipients will have significantly lower IDAS-GD total scores than those randomized to usual care at 4 & 8 weeks post enrollment.

Approach: Differences due to treatment condition will be tested for by repeated measures analyses (random regression/mixed model analysis) of depression symptoms (IDAS-GD). The primary test of interest is the time by group interaction on IDAS-GD scores. We will also assess potential within-group Listening Visits provider differences. We will review correlations between treatment exposure (the number and duration of contacts) in both groups to assess dose response relationship and adjust our analyses as necessary. Important biological variables, e.g. maternal age, will be assessed in this model.

Secondary, exploratory analyses will compare the effects of Listening Visits with usual care on additional indices on worry, stress, anxiety symptoms and satisfaction with NICU care. These secondary outcomes will be assessed using a simple t-test or Mann-Whitney test.

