Specific Aim #2: Compare the effect of Listening Visits with usual care on perception of nurse support as assessed by the Nurse Parent Support Tool. NPST scores will be compared between the two groups using a simple t-test (or Mann-Whitney, as necessary). We will also attempt to compare Listening Visits providers. Secondary analyses will assess relationship of scores on NPST with depression symptoms within and between groups.

Specific Aim #3 Compare the effect of Listening Visits with usual care on infant length of stay. We will use a log-rank test in the event that any infant is still in the hospital at the end of the study. If no censoring occurs, as we expect, the equivalent Wilcoxon-Mann-Whitney test will be used. As necessary, baseline CRIB-II score will be added as a covariate.

LV Telehealth: We will first compare the demographics of the women recruited through UIHC, Ronald McDonald House UIHC, Unity Point Health --Saint Luke's Hospital, OVIA Health or NICU Families of Eastern Iowa--Women's Wellness Center UIHC or NICU Parent Support blog to determine whether there are significant differences in the two samples. We will then evaluate the feasibility of delivering Listening Visits virtually by assessing uptake of this treatment among eligible women, assessing

depression symptoms at baseline, 4 weeks, and 8 weeks, and assessing their views of receiving this intervention via telehealth.

Specific Aim #1: Compare the effects of Listening Visits with usual care on depression symptoms as assessed by the Inventory of Depression & Anxiety Symptoms-General Depression Scale (IDAS-GD).

Hypothesis: LV recipients will have significantly lower IDAS-GD total scores than those randomized to UC at 4 & 8 weeks post enrollment.

Power: Assuming a large effect size ($d = 0.8$) at the endpoint (week 8), a moderate effect size at the midpoint ($d = 0.4$), with a moderate correlation in measures ($r = 0.7$), we have power of 0.82 for the interaction term of interest.

Secondary, exploratory analyses will compare the effects of Listening Visits with usual on additional indices on worry, stress, anxiety symptoms and satisfaction with NICU care. For secondary outcomes, we will only have sufficient power to detect large effects ($d \geq 0.8$).

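### The Aim 1 primary test makes no provision for baseline IDAS-GD; fitted in the ordinary way it is a change-from-baseline test that loses about 16% of the information at a common r = 0.7

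*SAP*

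**What the plan says.** The Aim 1 Approach in the SAP plans a repeated-measures mixed model (random regression) of IDAS-GD and names the test: "The primary test of interest is the time by group interaction on IDAS-GD scores". The hypothesis is about scores at the two follow-up visits: "Listening Visits recipients will have significantly lower IDAS-GD total scores than those randomized to usual care at 4 & 8 weeks post enrollment".

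On covariates, the same paragraph says "Important biological variables, e.g. maternal age, will be assessed in this model". Baseline IDAS-GD is not named there. The SAP's Preliminary Analyses refer in general terms to covariates related to missingness, and Aim 3 allows the baseline CRIB-II score as a covariate if needed. No section says whether baseline IDAS-GD is a response with a separate mean per arm, a response with a common mean, or a covariate.

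The Aim 1 power statement assumes d = 0.4 at the midpoint, d = 0.8 at week 8 and a single correlation of 0.7, and concludes that "we have power of 0.82 for the interaction term of interest". It gives no correlation structure, alpha or sidedness.

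The visit schedule is written out only for the telehealth cohort ("3 study assessments, at enrollment, and 4 and 8 weeks post enrollment"), but the Protocol's expanded aim describes that cohort as "Utilizing the same inclusion/exclusion criteria as the RCT and assessment schedule and instruments". I therefore take the RCT to have the same three visits.

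The Protocol reports that the RCT stopped in the pandemic and that the monitoring committee advised the team to "complete the analyses of the 45 out of 50 women in the RCT".

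**The concern.** A model with group, time and group-by-time terms estimates a separate baseline mean in each arm. With complete data, its interaction test then uses only the differences between each follow-up score and baseline. Randomisation makes the two true baseline means equal, and this model does not use that fact. Subtracting the whole baseline score amounts to a slope of 1, whereas the SAP's own correlation, with equal variances, implies a slope of 0.7. The excess adds baseline noise to the treatment comparison.

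What is at stake is precision on the trial's main question. RCT enrolment ended at 45 women, so more recruitment cannot restore it, while the baseline scores needed to recover it should already be in hand. Leaving the point unstated also lets the analyst choose between two models with different power.

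**Working it through.** **Inputs.** From the SAP: d = 0.4 (week 4), d = 0.8 (week 8), r = 0.7, and 25 per arm (stated under Aim 2, taken to apply to Aim 1). From the Protocol: 45 women in the RCT. Assumed: unit variance at each visit, no true baseline difference, two-sided 5%, no dropout, and a 22/23 split. Because the SAP gives one r and no structure, I show a common correlation, which is the plain reading, and an AR(1) decay, which is an assumption.

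**The SAP's 0.82.** It does not reproduce on the plain reading. With 25 per arm, a common r and separate baseline means, power is 0.947 (t) to 0.955 (normal) on 1 df, and 0.906 on 2 df (96 denominator df). With AR(1) it is 0.784 to 0.800 on 1 df, and 0.679 to 0.694 on 2 df. An AR(1) 2-df test with a common baseline mean gives 0.811 to 0.824. So the stated power cannot show which model was meant.

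**Information per unit of sample size**, as D′V⁻¹D with D = (0.4, 0.8):

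- *Common r, separate baseline means.* The covariance of the changes has variances 2(1 − 0.7) = 0.60 and covariance 0.30, with determinant 0.27. Information = (0.60×0.16 − 2×0.30×0.32 + 0.60×0.64)/0.27 = 0.288/0.27 = 1.067.
- *Common r, conditional on baseline.* Variances are 1 − 0.49 = 0.51 and covariance 0.70 − 0.49 = 0.21, with determinant 0.216. Information = (0.51×0.16 − 2×0.21×0.32 + 0.51×0.64)/0.216 = 0.2736/0.216 = 1.267. Loss = 1 − 1.067/1.267 = 15.8%.
- *AR(1), separate baseline means.* Variances are 0.60 and 1.02, covariance 0.51, determinant 0.3519. Information = 0.2208/0.3519 = 0.627.
- *AR(1), conditional on baseline.* Variances are 0.51 and 0.7599, covariance 0.357, determinant 0.2601. Information = 0.2195/0.2601 = 0.844. Loss = 1 − 0.627/0.844 = 25.7%.

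These are large-sample figures. When the baseline slope is estimated in 40,000 simulated trials of 50 women, the losses are about 14% and 24%.

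**Power with 45 women.** The noncentrality is (22×23/45) = 11.244 times the information: 11.99 and 14.24 under a common r, 7.06 and 9.49 under AR(1). I used noncentral t or F with 43 error df (separate baseline means) or 42 (baseline used). Because the assumed effects 0, 0.4, 0.8 are linear in time, the same noncentrality serves the 1-df trend test and the 2-df visit test.

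| Correlation | Test | Separate baseline means | Baseline used |
|---|---|---|---|
| Common r | 1 df | 0.92 | 0.96 |
| Common r | 2 df | 0.86 | 0.91 |
| AR(1) | 1 df | 0.74 | 0.85 |
| AR(1) | 2 df | 0.63 | 0.76 |

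Simulating 8,000 trials of 45 women with slope and covariance estimated gives almost the same 2-df gains: 0.86 to 0.90 under a common r and about 0.63 to 0.75 under AR(1). Type I error is about 0.05 for both tests.

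**Changing the degrees of freedom at the same time.** If the planned test is the 1-df trend and it were replaced by a baseline-adjusted 2-df joint test, power under a common r would go from 0.92 to 0.91 at d = 0.4/0.8, and from 0.72 to 0.68 at d = 0.3/0.6. Under AR(1) it would go from 0.74 to 0.76 and stay at 0.50. The gain depends on keeping the degrees of freedom fixed.

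**The case against.** The strongest reply is that the SAP does not say each arm keeps its own baseline mean. It is silent, the model can be fitted with a common mean, and the clause on covariates related to missingness could admit baseline IDAS-GD. This stands: the loss is conditional on the ordinary fit. Silence still needs correcting, because the two fits differ in power.

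A reader might infer that the SAP's own r = 0.7 implies a loss of up to 26%. It does not. One common correlation gives about 16%. The larger figure needs a baseline-to-week-8 correlation of 0.49, which neither document states.

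A reader might also infer that chance baseline imbalance biases the result. It does not. With a baseline difference of typical size, √(1/22 + 1/23) = 0.30 SD, the change-score estimate moves by 0.30 × (1 − 0.7) = 0.09 SD relative to the adjusted one, and the standard error already reflects this.

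Three further points stand. Under the plain reading, power is already 0.86 to 0.92 and the gain is about 4 to 5 points, which is modest for a pilot. A 2-df joint test should not be imposed, since the singular interaction term and the linear effects fit a 1-df trend. And changing a primary test after RCT enrolment has stopped carries a risk of post hoc choice, so the change is not free of downside.

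**Conclusion.** The point holds as one of efficiency and under-specification, not validity. The SAP makes no provision for baseline IDAS-GD in its primary model. As ordinarily fitted, the interaction gives up about 16% of the information at a common r = 0.7, or about 14% allowing for slope estimation in 50 women. If correlation decays as AR(1), the figures are about 26% and 24%.

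At 45 women and the SAP's effect sizes, with degrees of freedom unchanged, the cost is about 4 to 5 power points under a common r and 11 to 13 under AR(1). These figures rest on equal variances, a 22/23 split, two-sided 5%, no dropout, and baseline scores taken before allocation.

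**What to change.** State in the Aim 1 Approach how baseline IDAS-GD enters the model. Keep the mixed model and the three visits, but fit one baseline mean common to both arms, with group effects only after baseline. Using baseline IDAS-GD as a covariate with weeks 4 and 8 as outcomes is a close alternative.

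Say whether the intended test is the 1-df linear trend or the 2-df comparison by visit, and keep those degrees of freedom and the same alpha. Report the unconstrained interaction as a sensitivity analysis. Confirm that RCT baseline scores were collected before allocation, since the common mean depends on it.

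The cost is a sentence or two in the SAP and a small change of model code, with no new data. The downside is timing: the baseline-adjusted test should become primary only if outcomes by arm have not been examined. If they have, keep the stated test as primary and report the baseline-adjusted model as a labelled supplementary analysis.

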Specific Aim #2: Compare the effect of Listening Visits with usual care on perception of nurse support as assessed by the Nurse Parent Support Tool. With 25 participants in each group, we have 80% power to detect a large effect size ($d \geq 0.8$).

Specific Aim #3 for RCT ONLY Compare the effect of Listening Visits with usual care on infant length of stay. Power for this test will only be reasonable (i.e., ≥ 0.8) for large effects.

Specific Aim #3 OVIA trial/Noon News/U of Iowa email, UIHC and Unity Point Health -Saint Luke's Hospital Cedar Rapids; Ronald McDonald House UIHC and NICU Families of Eastern Iowa, Women's Wellness Center UIHC, NICU Parent Support blog/FB page : we will not collect information about infant length of stay in this modification. Instead of infant length of stay (the primary outcome for specific aim 3 in the grant application), we will examine the effect of LV on patient satisfaction (another outcome of practical utility in hospitals).

LV telehealth: The goal is to assess the feasibility through an open trial, no power analysis is required.

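### RCT Aim 3 does not define the length-of-stay event or say how an in-hospital infant death is handled; on the expected route a death would rank as a short, favourable stay

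*SAP*

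**What the plan says.** The Protocol's background section on Listening Visits lists infant length of stay among the primary outcomes. The SAP's Specific Aim #3 is to "Compare the effect of Listening Visits with usual care on infant length of stay". The rules that bear on it are these:

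- **Trigger for the log-rank test** (SAP, Specific Aim #3): "We will use a log-rank test in the event that any infant is still in the hospital at the end of the study".
- **Expected route** (same place): "If no censoring occurs, as we expect, the equivalent Wilcoxon-Mann-Whitney test will be used".
- **Dropouts** (SAP, RCT: Preliminary Analyses): "For the survival analysis, dropouts will be considered as censored".
- **Analysis set** (same place): "All randomized participants will be included in the analyses, an 'intent-to-treat' approach".
- **Severity adjustment** (SAP, Specific Aim #3): "As necessary, baseline CRIB-II score will be added as a covariate".

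Infant death as a study event appears once, in the Protocol's telehealth text on time commitment for research assessments: "In the event that an infant dies, mothers will not be asked to do further assessments". That sentence concerns the mother's questionnaires. For the telehealth cohort the SAP states "we will not collect information about infant length of stay in this modification", so the point below applies to the RCT only.

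**The concern.** Aim 3 reads a shorter stay as the better result. The Protocol presents longer stay as a possible harm of maternal distress, and improvement in length of stay as part of the case for spending nurse time. A stay can also be short because the infant died. Unless the plan separates the two endings, a day count treats them alike.

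Two things are at stake. An arm with more deaths could look as though its infants went home sooner. And because the handling is unstated, the choice would fall to the analyst after the data are seen, in a comparison small enough for one or two infants to matter.

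**Working it through.** **Where a death would go under the text**

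| How the death is classed | What the SAP then does | Consequence |
|---|---|---|
| Completed stay, nobody censored (expected route) | Wilcoxon-Mann-Whitney on days | Usually a short stay, ranked as favourable |
| Completed stay, another infant still in hospital | Log-rank, with the death as an event | Counted with the discharges |
| Dropout | Censored at death | Assumes discharge could still occur at the rate of those remaining |

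In the third row the death itself is the censoring, so the condition for the Wilcoxon-Mann-Whitney test fails. How one death is labelled can therefore decide which test is run. The CRIB-II covariate adjusts for baseline severity and does not say how a death is scored.

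**The plan's nearest figure.** The SAP gives no exact power for Aim 3, only that it is at least 0.8 for large effects. Its Aim 2 figure (25 per group, d = 0.8, 80%) reproduces at two-sided 5% (assumed): 0.807 by the normal formula and 0.791 by the noncentral t. That figure is not in dispute.

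**Leverage of one death.** The Protocol gives 45 women in the RCT. I assume one infant each and a 22/23 split.

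- Null SD of U = sqrt(n1 × n2 × (n1 + n2 + 1) / 12) = sqrt(22 × 23 × 46 / 12) = 44.04.
- An infant in the arm of 22 is compared with 23 others. Moving it from worst to best rank shifts U by at most 23, and 23 / 44.04 = 0.52 SD.
- On the scale of the probability of a shorter stay: 23 / (22 × 23) = 23 / 506 = 0.045.
- Two such deaths: 46 / 44.04 = 1.04 SD at most.
- At the planned 25 per arm: SD = sqrt(25 × 25 × 51 / 12) = 51.5, and 25 / 51.5 = 0.49 SD.

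These are upper bounds, because they take worst rank as the reference. Against a middle rank the shift is half: 11.5 / 44.04 = 0.26 SD.

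**Illustrative simulation.** No true effect on stay, 22/23, log-normal stays (log-mean 3.5, log-SD 0.8), two-sided 5% Wilcoxon-Mann-Whitney, time to death used as the stay. The entries are the chance of a significant result favouring one given arm. In the first two rows that is the arm with the deaths. Ranges are across repeated runs.

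| Deaths | 0 | 1 | 2 |
|---|---|---|---|
| All in that arm, at 0.5 to 3 days | about 2.4% | 3.9% to 4.0% | 5.8% to 6.3% |
| All in that arm, at a uniform fraction of the stay | about 2.4% | 3.0% to 3.4% | about 4.1% |
| Falling at random across both arms | 2.5% | 2.5% | 2.5% |

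**Effect on power.** With 25 per arm, a true d = 0.8 in favour of Listening Visits, log-SD 0.7 and death in the first half of the stay, power is 0.77 with no deaths. With two deaths in the Listening Visits arm only, it is 0.85 if time to death is the stay and 0.48 if death is ranked worst. With two deaths in usual care only, it is 0.55 and 0.85. Death counts, timing and stay distribution are all assumptions; none is in the documents.

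**The case against.** The strongest reply is that a reader might take the plan to prescribe scoring a death as an early discharge, and it does not. No sentence says so. Length of stay, the log-rank event and dropout are all undefined, and a bereaved mother could be classed as a dropout. This stands: the defect is an omission, and the favourable ranking is its consequence on the expected route. Dropout status does not rescue the plan, because censoring at death is informative.

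A reader might also infer that the Protocol anticipates infant deaths in the RCT. The only such sentence sits in the telehealth text, for a cohort in which length of stay is not collected. It shows awareness that NICU infants may die and nothing more.

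A third inference, that the rule inflates false-positive claims for Listening Visits, also fails. If treatment affects neither death nor stay, randomization makes the arms exchangeable and the test keeps its level, as the random-allocation row shows. The higher rates arise only when deaths are placed in one arm, and the largest need deaths within days. The intervention is empathic listening for mothers, and the documents suggest no mechanism for infant mortality.

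Finally, this is a pilot RCT powered only for large effects, and other estimands are defensible. Stay among survivors with deaths reported separately is one, though it conditions on an outcome after randomization. That choice is the sponsor's; leaving it unmade is the problem.

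**Conclusion.** The point holds as a gap in the RCT's Aim 3. The plan does not define what ends a stay or how an in-hospital death is handled, and followed literally none of its routes handles a death soundly. One death can move U by at most 0.52 null SD with 45 infants, assuming one infant per mother and a 22/23 split. The shift favours whichever arm has more deaths, which need not be Listening Visits. There is no inflation of type I error when deaths fall at random across arms, and no effect at all if no infant died. The documents give no death rate or timing, so the error-rate and power figures are illustrative and conditional on an imbalance in deaths. The correction is worth making because length of stay is a primary outcome and the change is small.

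**What to change.** Amend SAP Specific Aim #3, for the RCT, to state that:

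1. the outcome is time to discharge alive;
2. in the Wilcoxon-Mann-Whitney test, an infant who dies before discharge takes the worst rank, beyond the longest observed stay;
3. if the log-rank test is used, such an infant stays in the risk set to the end of follow-up as never discharged alive, and is neither an event nor a dropout;
4. infant deaths are reported by arm beside the length-of-stay result.

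The cost is a few sentences. No recruitment is needed, and discharge status should come with the stay data for the RCT infants. The result is unchanged if there were no deaths. The small downside is interpretive: the estimate describes time to discharge alive, not bed-days used. If the comparison has already been run, date the change and show both versions.

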Expanded aim June 2021 Ovia Health modification: recruit for the open trial preliminary evaluation of virtual Listening Visits through the Ovia Health parenting app. In this modification inclusion criteria are as follows: mothers 18 years of age or older, not currently receiving counseling and EPDS score 12-19 inclusive and EPDS item 10 rating < 2 and infant currently hospitalized in the NICU.

Enrolled women will be invited complete screening phase questionnaires via a redcap survey (see Screening Questionnaires in the attachment section)

- Participant contact form (to gather information for compensation)
- Demographics and Mental Health Treatment Questionnaire
- The Edinburgh Postnatal Depression Scale (EPDS)
- Patient Health Questionnaire (PHQ-9)

Participants whose responses on screening phase questionnaires who meet the following inclusion criteria will be invited to enroll in the open trial evaluation of telehealth Listening Visits delivered by a NICU nurse.

EPDS score= 12 through 19, inclusive; with a rating of 1 or less on EPDS item #10

Women is not currently receiving counseling services

Study participation is complete among women whose responses on the screening phase questionnaires who do not meet the above criteria or among women who do not wish to enroll in the open trial.

The participants in the open trial will be women who have responded to the OVIA Health ad or email, the UI mass email or the flier in the UIHC NICU or Unity Point-Health-St. Luke's

Participants will be 18 years of age or older, whose babies are currently hospitalized on a Neonatal Intensive Care Unit meeting the following eligibility criteria:

Score of 12 through 19 (inclusive of 19) on the Edinburgh Postnatal Depression Scale and a rating < 2 on item 10 Not currently receiving counseling

Screening questions

-Newborn currently hospitalized in the NICU

-18 years of age or older

-Not currently receiving counseling

-Edinburgh Postnatal Depression Scale (repeated for assessment 2 and 3 in open trial)

Open Trial

Contact information (email, phone, and postal address) (Assessment 1 only)

Demographics &treatment use questionnaire (Assessment 1 only)

EPDS (Enrollment, assessment 2 and assessment 3)

Depression Symptoms in the Past Two Weeks: (Inventory of Depression and Anxiety Symptoms-General Depression Scale-IDAS-GD (assessment 1, 2, 3)

Neonatal Satisfaction Survey (assessment 2)

-Satisfaction with Care and Use of Mental-Health Service (assessment 2)

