1. Immediately after enrolling into the open trial, participants will complete questions pertaining to her contact information (email, phone number and postal address) as well as the baseline assessment questionnaires. The REDCap survey will be programmed to send an email to a member of the research team when a new participant has enrolled. A member of the research team will give the woman's email and phone number to the Listening Visits nurse, who will contact the participant to arrange the first Listening Visits zoom session. A member of the research team will use the address to provide compensation for the completion of the baseline assessment.
2. Listening Visits will be provided by a NICU nurse research team member virtually. Women who enroll into the open trial will be invited to meet virtually with a NICU nurse up to 6 times, approximately twice per week, for about 45 to 60 minutes for the listening sessions. The zoom platform will be used to connect with women. This is the platform used by the Seashore Clinic at the University of Iowa to conduct psychotherapy sessions. It is a platform that women are likely familiar as are the nurses. When nurses connect with women via zoom, they will check with her if it is still a good time for her to talk and that she feels she has sufficient privacy. If no, then a different time will be arranged. The nurse will send the woman a zoom link for each session. With consultation from IT on how to set up the zoom session so that it is compliant and secure, the NICU Listening Visit nurses will send the link to the participant via email. Participants will meet for up to six sessions with the NICU nurse for the Listening Visits. This intervention is nondirective; thus, the specific focus of each session is directed by the needs of the participant. Each session provides a time for the woman to discuss her concerns with a nonjudgmental listening who utilizes reflective listening and problem solving to provide an empathic interchange. Early sessions are oriented toward listening while in later sessions the nurse and woman work collaboratively to identify specific problems and generate solutions. The last session involves a summary of the sessions.

LV Telehealth Time Period Over Which Procedures Will Occur

-From IRB approval through end of study funding

LV Telehealth Time Commitment --Research Assessments:

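### Open-trial Aim 3 sets out to examine an effect of Listening Visits on satisfaction, but one arm measured once, at week 4, can only describe a level

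*SAP*

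**What the plan says.** The SAP's Specific Aim #3 entry for the OVIA and other open-trial recruitment sources drops infant length of stay, which will not be collected, and puts in its place: "we will examine the effect of LV on patient satisfaction (another outcome of practical utility in hospitals").

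The Protocol describes the cohort to which this applies:

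- **Design.** The expanded aim is to "evaluate the feasibility of delivering Listening Visits virtually, in an open trial design".
- **Treatment.** "Women who enroll into the open trial will be invited to meet virtually with a NICU nurse up to 6 times". No control group or allocation is described.
- **Satisfaction measures.** The Open Trial list has two: "Neonatal Satisfaction Survey (assessment 2") and "Satisfaction with Care and Use of Mental-Health Service (assessment 2").
- **Schedule.** There are "3 study assessments, at enrollment, and 4 and 8 weeks post enrollment". Assessment 2 is therefore week 4.

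The SAP's LV Telehealth paragraph first compares demographics by recruitment source. It then names three things to assess: uptake, depression symptoms at the three assessments, and women's views of telehealth delivery. The SAP's closing LV telehealth line gives feasibility as the goal and says that no power analysis is needed.

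**The concern.** An effect needs a contrast, either with women who did not receive LV or, more weakly, with the same women before they received it. The open trial plans neither for satisfaction.

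Elsewhere in the SAP, effect means LV compared with usual care, so a reader could reasonably take it that way here. The SAP also presents satisfaction as useful to hospitals. If the aim is followed as written, an uncontrolled week-4 score could be reported to that audience as something telehealth LV achieved.

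The Protocol's own background section on Listening Visits warns that mood improvement seen in the earlier uncontrolled NICU trial cannot be firmly credited to LV. That warning concerned a before-and-after change. A single score supports less.

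**Working it through.** The documents give no sample size, power or effect size for open-trial satisfaction, so there is no stated figure to reproduce. The check is to count what the design can estimate.

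**Contrasts available**

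| Element | Source | Count |
|---|---|---|
| Comparator arms | Protocol, Expanded aim and open-trial procedures | 0 |
| Satisfaction instruments with a pre-LV score | Protocol, Open Trial list | 0 of 2 |
| Assessments that include satisfaction | Same list | 1 of 3 |
| Assessments that include EPDS and IDAS-GD | Same list | 3 of 3 each |
| Telehealth analysis elements that name satisfaction | SAP, LV Telehealth | 0 of 3 |
| Comparisons with another sample on satisfaction | SAP, LV Telehealth | 0 (demographics only) |

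One arm gives no between-group difference, and one time point gives no change. The week-4 mean or distribution, with its confidence interval, is what remains. The aim also does not say which of the two instruments is meant, and no summary or test is given.

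**Is week 4 after treatment?** This is a secondary point. Sessions are offered "up to 6 times, approximately twice per week". Enrollment does not fix their start, because the contact details go to the nurse, "who will contact the participant to arrange the first Listening Visits zoom session". Six sessions have 5 intervals, so:

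- span in days = 5 / (sessions per week) × 7
- latest first session for all six to end by day 28 = 28 − span

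| Sessions per week | Span (days) | Latest first session (days after enrollment) |
|---|---|---|
| 2.0 (stated as approximate) | 5 / 2.0 × 7 = 17.5 | 28 − 17.5 = 10.5 |
| 1.5 (assumed) | 5 / 1.5 × 7 = 23.3 | 28 − 23.3 = 4.7 |
| 1.25 (assumed) | 5 / 1.25 × 7 = 28.0 | 28 − 28.0 = 0 |

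Below 1.25 per week, a sixth session always falls after week 4. Assessment 2 therefore cannot be assumed to follow completed LV for every woman.

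**The case against.** The strongest reply is that this is loose wording in a plan that already limits itself. No hypothesis, test or power is attached to open-trial satisfaction, the stated goal is feasibility, and the Protocol shows that the team understands the limits of uncontrolled data. That bears on severity. It does not make the sentence right, and an SAP is the place to settle such wording.

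Other points on that side:

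- **Views of telehealth may include satisfaction.** Among the listed measures, the two satisfaction instruments are the likeliest source of those views, so the 0 of 3 count is a literal reading. The items are not shown. If one instrument asks about LV itself, collecting it only afterwards is normal. The result is still a level.
- **Other contrasts are conceivable.** The expanded aim reuses the RCT's instruments and schedule, so a comparison with RCT usual care might be possible. A nurse log is listed, so an association with number of sessions might be too. Neither is planned for satisfaction. The first would be confounded by recruitment source, delivery mode and period, the second by self-selection into more sessions.
- **The timing arithmetic is not needed.** This is correct: with every session finished by week 4 there would still be one arm and one score. The tighter margins rest on assumed rates, and six sessions is a maximum.
- **The RCT is a limited fallback.** This also stands. The Protocol reports 45 of 50 women in the RCT. With an assumed 23/22 split and two-sided alpha of 0.05 (neither stated), power at d = 0.8 is about 0.75 by noncentral t, against 0.79 with 25 per group. The RCT outcome is satisfaction with NICU care, which may differ from what the open-trial aim calls patient satisfaction.

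**Conclusion.** The concern holds. As planned, the open trial cannot estimate an effect of LV on satisfaction. It can describe how satisfied the responding women were four weeks after enrollment, some possibly before their sessions had ended.

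The conclusion rests on the single-arm design, the listing of both instruments at assessment 2 only, and the absence of a planned comparator. The one inference is that assessment 2 is week 4, which follows from the order of the three assessments. The assumed session rates affect only the timing remark.

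This should be fixed, because it changes what the trial may conclude about an outcome aimed at hospitals. The feasibility goal and the RCT analyses are unaffected.

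**What to change.** Reword the open-trial Aim 3 in the SAP along these lines:

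> Satisfaction at assessment 2 on [named instrument(s)] will be described as a mean with SD and 95% CI, with the number responding out of the number enrolled. No effect of LV will be inferred.

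Add that any claim about an effect of LV on satisfaction comes from the randomised comparison with usual care, set out among the secondary analyses under the SAP's Aim #1, and concerns LV as delivered in the RCT, not telehealth LV. If the sponsor wants a comparison with RCT usual care, it should be specified in advance and labelled non-randomised and exploratory.

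The recommended rewording needs no new data. The sponsor gives up an effect claim for telehealth LV that the design cannot support. The randomised comparison that remains does not cover telehealth and, by the SAP's own statement, is adequately powered only for large effects (d of 0.8 or more).
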